		PBO + Dexamethasone + RDV	x	xx.x	xx.x, xx.x	xx.x	xx.x, xx.x	x	xx.x	xx.x, xx.x	xx.x	xx.x, xx.x
	Day 5	Baricitinib + PBO + RDV	x	xx.x	xx.x, xx.x	xx.x	xx.x, xx.x	x	xx.x	xx.x, xx.x	xx.x	xx.x, xx.x
		PBO + Dexamethasone + RDV	x	xx.x	xx.x, xx.x	xx.x	xx.x, xx.x	x	xx.x	xx.x, xx.x	xx.x	xx.x, xx.x
	Day 8	Baricitinib + PBO + RDV	x	xx.x	xx.x, xx.x	xx.x	xx.x, xx.x	x	xx.x	xx.x, xx.x	xx.x	xx.x, xx.x
		PBO + Dexamethasone + RDV	x	xx.x	xx.x, xx.x	xx.x	xx.x, xx.x	x	xx.x	xx.x, xx.x	xx.x	xx.x, xx.x
	Day 11	Baricitinib + PBO + RDV	x	xx.x	xx.x, xx.x	xx.x	xx.x, xx.x	x	xx.x	xx.x, xx.x	xx.x	xx.x, xx.x
		PBO + Dexamethasone + RDV	x	xx.x	xx.x, xx.x	xx.x	xx.x, xx.x	x	xx.x	xx.x, xx.x	xx.x	xx.x, xx.x
	Day 15	Baricitinib + PBO + RDV	x	xx.x	xx.x, xx.x	xx.x	xx.x, xx.x	x	xx.x	xx.x, xx.x	xx.x	xx.x, xx.x
		PBO + Dexamethasone + RDV	x	xx.x	xx.x, xx.x	xx.x	xx.x, xx.x	x	xx.x	xx.x, xx.x	xx.x	xx.x, xx.x
	Day 29	Baricitinib + PBO + RDV	x	xx.x	xx.x, xx.x	xx.x	xx.x, xx.x	x	xx.x	xx.x, xx.x	xx.x	xx.x, xx.x
		PBO + Dexamethasone + RDV	x	xx.x	xx.x, xx.x	xx.x	xx.x, xx.x	x	xx.x	xx.x, xx.x	xx.x	xx.x, xx.x

Continue for all parameters...Table

N = Number of subjects in the As Treated Population with laboratory data available for the parameter at the specified study visit.

Programming Note: Include all lab parameters in this table except d-dimer and CRP which are in table.

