3.3.2. Study Day and Time to Event

Use of "Day 29" or "Day 15" are references to actual study days and represent 28 and 14 days post-randomization, respectively. References to visits such as "Study Visit Day 29" and "Study Visit Day 15" pertain to protocol-defined visits which may occur on any day within the defined visit window and not necessarily on Day 29 and Day 15.

Time-to-event endpoints are based on actual study days, e.g., Day 29 or Day 15. Endpoints that are not specifically defined as a time-to-event are based on Study Visits, irrespective of the study day upon which the visit was conducted. As a result, time-to-event endpoints at Day 15 and Day 29 may not match corresponding Clinical Status Ordinal Scores at Study Visit Day 15 and Study Visit Day 29. For example, all subjects with Clinical Status in Category 7 or 8 recorded for Study Visit Day 29 performed on or after Day 31 may not count as events by Day 29 unless there is additional corroborating data (e.g., Death or Supplemental Oxygen Case Report Forms).

3.3.3. Mechanical Ventilation-Free Survival at Day 29

Subjects who do not report an ordinal score in Category 8 (Death) or Category 7 (hospitalized on invasive mechanical ventilation or ECMO) at any point following randomization up to and including Day 29 will be

considered to have survived free from mechanical ventilation. The proportion of subjects who survive through Day 29 free from mechanical ventilation will be estimated using a Kaplan-Meier method, allowing definition of time-to-event and time-to-censoring for all subjects.

The time-to mechanical ventilation or death is defined as the elapsed time in days from randomization to the earliest day at which the subject requires mechanical ventilation or dies. The day the subject requires mechanical ventilation is defined as the first day reporting an ordinal score in Category 7. Note (as in Section 3.3.4), this should be the date the subject is assessed, and not the date the score is reported. The time-to-event for subjects discharged to hospice or other end-of-life care prior to Day 29, but for whom a death date is unknown and with Day 60 data unavailable, will be the number of days from randomization to discharge.

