3.3.7. Recovery and Time to Recovery

A Secondary Endpoint measure requires the time to recovery assessed through Study Visit Day 29. Recovery will be defined as having a value of 1, 2, or 3 on the 8-point ordinal Clinical Status score. The time to recovery will be defined as the elapsed time (in days) from randomization to the earliest day at which a subject reaches recovery. Note that since clinical status assessments are recorded as defined in Section 4.3, the day that is being assessed (not necessarily the day the response is collected) will be used to determine the timing of events. For example, a subject with a score of 5 recorded on study days 1-3 and a score of 3 recorded on study day 4 will have a time to recovery equal to 3 days. It is also possible that a subject has a clinical status ordinal score > 3 reported for a particular day but was subsequently discharged on the same day. If a subject is discharged to a location other than hospice or another hospital the subject will be considered recovered at the time of discharge but may be reviewed by the Endpoint Review Committee, if other data suggests the subject may not be recovered (e.g., the subject is re-admitted). If a subject is discharged to hospice or another hospital, re-admitted, or is a special case where recovery handling may be unclear, the subject's data will be reviewed by the Endpoint Review Committee to make the determination of whether the subject should be considered recovered and, if so, at what time point in the analyses. Subject data to be reviewed as part of this determination will include the reported clinical status scores while hospitalized, where the subject was discharged to (e.g. private residence, rehabilitation facility, long-term care/nursing home, comfort and care), and any information regarding readmittance. Additional information may be solicited to assess recovery.

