Any subjects that are lost to follow-up or terminated early prior to an observed recovery will be censored at the day of their last observed assessment. Subjects who complete follow-up but do not experience recovery will be censored at the day of their Study Visit Day 29. All deaths that occur on or before Study Visit Day 29 (and prior to any observed recovery) will be considered censored at Day 29. Note that we do not expect many subjects to worsen after discharge. However, we will evaluate whether any discharged subjects subsequently experience a worse clinical status and sensitivity analyses will be conducted accordingly. For these analyses, subjects who recover but are later re-admitted for COVID-19 will not be considered a recovery but will instead be censored at 28 days.

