6. GENERAL STATISTICAL CONSIDERATIONS

6.1. General Principles

This is a double-blind, placebo controlled randomized trial with a two-sided type I error rate of 0.05. Secondary hypotheses have been ordered according to relative importance. These will be described according to the appropriate summary statistics, e.g.:

- Percentages/proportions/odds ratios for categorical data. For tabular summaries of percentages/proportions, the denominator (e.g. number of subjects with non-missing data) will be displayed.
- Means, median, and range for continuous data, median for time-to-event data.

Confidence intervals will be generated; for the primary analysis, the confidence level will take into account the group-sequential design of the trial (see Section 6.6 and Section 8.1) whereas 95% confidence intervals will be generated for secondary and exploratory outcomes. Proportions will be estimated using the Kaplan-Meier Day 29 survival estimate with Wald-type confidence intervals assuming large-sample normality with standard errors estimated using Greenwood's formula for variance. For hazard ratio and odds ratio estimates, Wald confidence intervals will also be used. For other efficacy outcomes (e.g. proportions), Wilson or Score confidence intervals will be used. For safety outcomes, exact (e.g. Clopper-Pearson) confidence intervals will be used.

When calculating treatment effects (e.g., differences, hazard ratios, odds ratios) and when using treatment arm as a covariate in regression modeling, the baricitinib + placebo + remdesivir arm will be used as the reference group. For regression modeling that uses strata variables defined in Section 6.4, the first stratum listed for each variable in that section will be used as the reference group.

For the final comparison of Day 29 mechanical ventilation free survival, the following SAS pseudocode will be used to obtain Kaplan-Meier survival estimates, standard errors and confidence intervals, for each treatment within strata. Survival estimates and standard errors will be used to calculate the test statistic and compared to a standard normal distribution as in Section 8.1.1.

```
proc lifetest data=dataset plots=(s) method = km outsurv = survests;
  time TimeVariable * CensorVariable(1);
  strata TreatmentVariable StrataVariable;
run;
```

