Repeat for the As Treated Population.

N= Number of subjects in the specified treatment group, actual baseline ordinal score, and analysis population.
n = Number of recovered subjects.
Difference is the difference in the restricted mean recovery time between PBO + Dexamethasone + RDV to Baricitinib + PBO + RDV.
^a Tau is the truncation time point for the Restricted Mean Survival Time analysis and is equal to the minimum of the largest observed times in each group

Programming Notes:

Within an actual baseline ordinal score stratum:

```
proc lifetest data=enrevent plots=(rmst) method=breslow rmst(cl);
by stratum;
time evntday * Censor(1);
strata trtcode /diff=all;
ods output rmst=rmst;
run;
```

Stratified by actual Baseline Ordinal Score (“Baseline Ordinal Score 5 or 6” row).

```
proc lifetest data=enrevent plots=(rmst) method=breslow rmst(cl);
time evntday * Censor(1);
strata trtcode CRSEVERE /diff=all;
ods output rmst=rmst;
run;
```

Table 35: Summary of Recoveries and Deaths by Day 29 – mITT Population

Grouping Variable	Actual Baseline Ordinal Score	Treatment Group	Recovered ^b		Did Not Recover		Deaths ^b		Died or Not Recovered		
			n	%	n	%	n	%	n	%	
Actual Baseline Ordinal Score	5	Baricitinib + PBO + RDV (N=X)	x	x	x	x	x	x	x	x	
		PBO + Dexamethasone + RDV (N=X)	x	x	x	x	x	x	x	x	
	6	Baricitinib + PBO + RDV (N=X)	x	x	x	x	x	x	x	x	
		PBO + Dexamethasone + RDV (N=X)	x	x	x	x	x	x	x	x	
	Baseline Ordinal Score 5 or 6	Baricitinib + PBO + RDV (N=X)	x	x	x	x	x	x	x	x	
		PBO + Dexamethasone + RDV (N=X)	x	x	x	x	x	x	x	x	
	Any Baseline Ordinal Score ^a	Baricitinib + PBO + RDV (N=X)	x	x	x	x	x	x	x	x	
		PBO + Dexamethasone + RDV (N=X)	x	x	x	x	x	x	x	x	
Repeat for duration of symptoms categories in Section 6.4											
N= Number of subjects in the mITT Population.											
^a [X] additional subjects are included in the ‘Any Baseline Ordinal Score’ row that were enrolled with a baseline ordinal score of 4. [Include as applicable]											
^b [Number] subjects recovered but subsequently died. These X subjects are included in both the recoveries and also in the deaths counts.											

Programming Note: For the categories of “Recovered”, “Did Not Recover” and “Deaths”, subjects who recover but subsequently die will be classified under “Recovered” and “Deaths”. If there are cases of this, footnote b will be added.

Table 36: Time to One or Two Category Improvement on the 8-Point Ordinal Scale by Treatment Group, Actual Baseline Ordinal Score 5 or 6

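### Table 34's restricted-mean recovery analysis uses the Breslow curve on tied whole-day times and a truncation time that can drift past 28 days (minor, exploratory)

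*SAP*

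**What the plan says.** The programming notes under Table 34 (Appendix 1) give two calls, one within each baseline score and one for scores 5 and 6 combined. Both begin "proc lifetest data=enrevent plots=(rmst) method=breslow rmst(cl", and neither has a `tau=` option. Footnote a sets tau "equal to the minimum of the largest observed times in each group", and the table prints tau. The title places the analysis by Day 29. Section 3.3.2 says that Days 29 and 15 "represent 28 and 14 days post-randomization, respectively", and bases time-to-event endpoints on actual study days.

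Section 3.3.7 counts recovery in whole days: "a score of 3 recorded on study day 4 will have a time to recovery equal to 3 days". On censoring it says "Subjects who complete follow-up but do not experience recovery will be censored at the day of their Study Visit Day 29", and for deaths "All deaths that occur on or before Study Visit Day 29 (and prior to any observed recovery) will be considered censored at Day 29". Section 3.3.2 allows a study visit to fall anywhere in its window and uses Day 31 or later as its example.

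Elsewhere the SAP uses Kaplan-Meier. Section 8.1.2.4 and Figures 15 to 17 plot recovery that way, and the code for the primary endpoint in Section 6.1 begins "proc lifetest data=dataset plots=(s) method = km outsurv = survests". Section 8.2.5 labels the restricted-mean analysis exploratory.

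**The concern.** Two choices look out of line with the rest of the SAP.

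First, on a day when d of Y patients at risk recover, the Breslow curve is multiplied by exp(-d/Y) and the Kaplan-Meier curve by 1 - d/Y. The former is always larger, and the gap matters when many patients recover on the same day. The restricted means in Table 34 would then not be the areas under the curves shown for the same endpoint. No reason is given for the switch.

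Second, tau follows the data. Sections 3.3.3 and 3.3.6 hold ventilation-free survival and time to death at actual Day 29 even when the visit is late. Section 3.3.7 has no such cap for patients who complete follow-up unrecovered. A table labelled by Day 29 could therefore report a mean over a longer horizon, set by when a few late visits took place.

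**Working it through.** The SAP gives no restricted mean or value of tau, so there is no figure to reproduce.

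**Inputs.** Medians from Section 2: 5 and 6 days (low-flow oxygen, score 5), 10 and 18 days (high-flow or non-invasive ventilation, score 6), 7 and 8 days overall. They come from the preceding trial stage, so they only illustrate plausible recovery speeds. Assumed shares p never recovering: 6% and 8% (score 5), 25% and 35% (score 6), 12% and 15% (overall).

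**Model.** On whole days S(t) = p + (1 - p)q^t, with q = [(0.5 - p)/(1 - p)]^(1/median). The Kaplan-Meier area to tau is the sum of S(t) for t = 0 to tau - 1. The Breslow area replaces S(t) by the exponential of minus the summed daily hazards.

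**One arm by hand.** Median 5, p = 0.06: q = (0.44/0.94)^(1/5) = 0.859. On day 1 the hazard is 0.94 × (1 - 0.859) = 0.132; Kaplan-Meier steps to 0.868 and Breslow to exp(-0.132) = 0.876. Over 28 days the Kaplan-Meier area is 28 × 0.06 + 0.94 × (1 - q^28)/(1 - q) = 8.26 days. Breslow gives 8.73, an excess of 0.47.

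**Estimator, tau = 28 (days)**

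| Row | Kaplan-Meier | Breslow | Excess per arm | Difference, KM to Breslow |
|---|---|---|---|---|
| Score 5 | 8.26, 9.56 | 8.73, 9.98 | 0.47, 0.42 | -1.30 to -1.25 |
| Score 6 | 13.88, 17.26 | 14.16, 17.42 | 0.28, 0.16 | -3.38 to -3.26 |
| Overall | 10.87, 11.93 | 11.25, 12.27 | 0.38, 0.34 | -1.06 to -1.02 |

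The excess shows at the one decimal that Table 34 reports. In the difference it mostly cancels: 0.03 (overall medians with no share never recovering) to 0.12 day at tau = 28, at most 0.14 at tau = 35 (score 6), and zero if the arms are equal.

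**Horizon.** Trials were simulated with 500 (score 5) or 250 (score 6) patients per arm and 30% of Day 29 visits late. Size, share and lateness are all assumed.

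| Visits late by | Mean tau, score 5 | Mean tau, score 6 | Score 6 KM difference, 28 days to floating tau |
|---|---|---|---|
| none | 28.0 | 28.0 | -3.41, unchanged |
| 1-3 days | 30.8 | 31.0 | -3.40 to -3.80 |
| 1-6 days | 33.2 | 33.8 | -3.34 to -4.04 |

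For score 5 with visits 1-6 days late, the difference goes from -1.28 to -1.42. A simple exponential check with control median 18 days agrees: moving tau from 28 to 31 changes the absolute difference from 3.18 to 3.60 days at a hazard ratio of 1.5, and from 4.68 to 5.26 at 1.8.

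**Does this need recoveries after Day 29?** No. If the curves are flat after 28 days, the difference still grows by (tau - 28) times the gap between them. At hazard ratio 1.5 the unrecovered shares at 28 days are 0.340 and 0.198, so 3.18 + 3 × 0.142 = 3.61.

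**Deaths.** Section 3.2 counts recovery up to Day 29; Section 3.3.7 assesses it through Study Visit Day 29. Under the first reading nothing happens after 28 days, and censoring deaths at 28 does no harm. Under the second, deaths leave the risk set at 28 days, before any later recovery, and no longer count as never recovered.

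**The case against.** The best defence is that nothing is hidden and little depends on it. Footnote a states the rule, tau is printed, and both arms in a row share it. The 28 days is inferred from the title and Section 3.3.2; footnote a does not state it. All of that stands.

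A reader might infer that Breslow biases the treatment comparison. The figures do not support this: with standard errors of about 0.52 day (score 5) and 0.94 day (score 6) at the assumed sizes, the shifts of 0.05 and 0.12 are about a tenth of a standard error, toward zero.

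A reader might also take the 12-13% growth in the difference at tau = 31 as bias. It is not: a longer horizon gives a larger restricted-mean difference. As a share of the horizon it hardly moves (3.18/28 = 11.4%; 3.60/31 = 11.6%). The fault is that the horizon is neither fixed in advance nor the one in the title.

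Nor do the documents show that the score 5 and score 6 rows will have different horizons. They may, but in the simulations the mean values of tau were close, and Section 8.2.5 plans no comparison across rows.

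Finally, neither METHOD nor tau enters the stratified log-rank test of Section 8.1.2.4, which carries the inference on recovery.

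**Conclusion.** The point holds as a minor one. The Breslow option follows from the text alone and makes the restricted means in Table 34 too high relative to the SAP's own Kaplan-Meier curves, by roughly 0.15 to 0.5 day per arm and less in score 6. Its effect on the arm difference is about 0.03 to 0.14 day. These sizes rest on the medians in Section 2 and on the assumed shares never recovering.

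The drift in tau is conditional. It occurs only if each compared group has an observed time beyond 28 days, in practice an unrecovered patient seen late. The SAP anticipates late visits but gives no window, so the size cannot be fixed. The concern about deaths is narrower still and needs recoveries after Day 29 to be counted. The analysis is exploratory, has no p-value column and lies outside the testing hierarchy, so no confirmatory conclusion is threatened.

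**What to change.** In both Table 34 calls, replace the Breslow option with `method=km` and use `rmst(cl tau=28)`. Censor at 28 days everyone unrecovered by actual Day 29, preferably by adding to Section 3.3.7 the cap already used in Sections 3.3.3 and 3.3.6. This also settles whether later recoveries count. Reword footnote a to tau = 28 days for all rows.

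While editing, check the second call: its strata statement lists treatment and baseline score together, which forms arm-by-score groups. Changing METHOD and tau will not by itself give the single estimate per arm that the combined row needs.

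The cost is two code options, one censoring sentence and one footnote, with no new data.

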- Grade 3 and 4 treatment emergent adverse events
- Incidence and number of discontinuation or temporary suspension of study product
- WBC with differentials, hemoglobin, platelets, creatinine, glucose, total bilirubin, ALT, AST, INR, on Day 1; Days 3, 5, 8, and 11 (while hospitalized); and Days 15 and 29 (if attends in-person visit or still hospitalized).

Exploratory Endpoints

- Alternate DOOR scales

None of the remaining exploratory endpoints will be described in this SAP, but they include the following:

- Virology endpoints:
 - Qualitative and quantitative polymerase chain reaction PCR for SARS-CoV-2 in OP swab on Day 1; Days 3, 5, 8, and 11 (while hospitalized); and Days 15 and 29 (if attends in-person visit or still hospitalized).
 - Qualitative and quantitative PCR for SARS-CoV-2 in blood on Day 1; Days 3, 5, 8, and 11 (while hospitalized).
- Serology endpoint: SARS-CoV-2 antibody titers on Day 1, 8, and 29.

- Immunophenotype endpoints:
 - Proteomic analysis of cytokines, markers of inflammation, and other circulating proteins on Day 1; Days 3, 5, 8, and 11 (while hospitalized) and Day 29.
 - Additionally, in a subset of subjects who consent to genetic testing, transcriptomic analysis of RNA in whole blood and individual immune cells on Days 1, 3, 8, and 29.
- Chronic Clinical Sequelae: Ordinal score, incidence of supplemental oxygen use and physical disability (more than baseline pre-COVID-19 status), readmission to hospital; proportion of subjects with new diagnoses including deep venous thrombosis (DVT), infections, post-traumatic stress disorder (PTSD), anxiety and/or depression.

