6.3.2. Modified Intention-to-Treat (mITT) and As Treated Populations

The modified intention-to-treat (mITT) population includes all subjects who were randomized. mITT subjects will be classified by their randomized treatment assignment and actual baseline ordinal score ordinal stratum (i.e., the stratum corresponding to their baseline ordinal score, not necessarily the stratum within which the subject was randomized at enrollment).

The As Treated population includes all randomized subjects who received the study product, even if only one dose was administered.

For As Treated analyses of efficacy outcomes, subjects will be classified by their actual treatment assignment and their actual baseline ordinal score, unless otherwise specified in the table or figure shell. Note that if no subjects are administered the incorrect treatment and all subjects receive at least one dose of baricitinib/placebo, dexamethasone/placebo, the As Treated efficacy analysis will not be performed as they will be identical to the mITT analyses.

For As Treated analyses of safety outcomes, concomitant medications, and medical history, subjects will be classified by their actual treatment assignment and actual baseline ordinal score stratum.

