9.6. Clinical Laboratory Evaluations

Clinical safety laboratory adverse events are collected Day 1, 3, 5, 8, 11 and Day 15 and 29 if able to return to clinic or still hospitalized. Parameters evaluated include white blood cell count, absolute neutrophil count, eGFR, platelet count, hemoglobin concentration, creatinine, glucose, total bilirubin, ALT, AST, INR, d-dimer, and CRP. Laboratory safety parameters will be graded according to the Division of AIDS (DAIDS) Table for Grading the Severity of Adult and Pediatric Adverse Events, version 2.1 (July 2017). For sites that do not

report an upper (lower) limit for the value of a laboratory parameter, the median of the reported upper (lower) limits across the other sites will be used. Medians and calculated LLN/ULN used if any, will be documented in the ADaM documentation. Vitamin D is collected on Day 1 and is not graded, but results will be summarized.

The distribution of Grade 3 and 4 chemistry and hematology laboratory results by maximum severity, time point, actual baseline ordinal score and treatment group will be presented ([Table 88](#)). Treatment-emergent laboratory abnormalities will be summarized by parameter and grade ([Table 89](#)).

Descriptive statistics including mean, median, standard deviation, maximum, and minimum values and change from baseline by time point, for all and each chemistry and hematology laboratory parameter will be summarized by actual baseline ordinal score and treatment arm ([Table 51](#) and [Table 90](#)). Changes in chemistry and hematology laboratory values will be presented in line graphs over time with median, Q1 and Q3 plotted by actual baseline ordinal score and treatment arm ([Figure 34](#)).

Listings will provide a complete listing of individual chemistry and hematology laboratory results with applicable reference ranges ([Listing 23](#)).

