	Day 5	Baricitinib + PBO + RDV	x	x	X	x	x	x	x		
		PBO + Dexamethasone + RDV	x	x	X	x	x	x	x		
	Day 8	Baricitinib + PBO + RDV	x	x	X	x	x	x	x		
		PBO + Dexamethasone + RDV	x	x	X	x	x	x	x		
	Day 11	Baricitinib + PBO + RDV	x	x	X	x	x	x	x		
		PBO + Dexamethasone + RDV	x	x	X	x	x	x	x		
	Day 15	Baricitinib + PBO + RDV	x	x	X	x	x	x	x		
		PBO + Dexamethasone + RDV	x	x	X	x	x	x	x		
	Day 29	Baricitinib + PBO + RDV	x	x	X	x	x	x	x		
		PBO + Dexamethasone + RDV	x	x	X	x	x	x	x		
	Maximum Severity Post Baseline		x	x	X	x	x	x	x		
			x	x	X	x	x	x	x		
Each parameter will be summarized individually similar to the above...											
The “Max Post Baseline” rows indicate the maximum severity experienced by each subject at any time point post baseline, including unscheduled assessments and assessments beyond Day 29.											
N = Number of subjects in the As Treated Population											

Programming Note: Vitamin D, D-dimer and CRP results are not included in this table. Include all lab parameters that are being graded in this table.

Table 89: Treatment-Emergent Laboratory Abnormalities - As Treated Population, Actual Baseline Ordinal Score of 5 or 6

Laboratory Parameter	Maximum Post Baseline Grade	Baricitinib + PBO + RDV (N=X)			PBO + Dexamethasone + RDV (N=X)		
		N	n	%	N	n	%
Any Parameter	1	x	x	x	x	x	x
	2	x	x	X	x	x	x
	3	x	x	X	x	x	x
	4	x	x	X	x	x	x
	Any Grade	x	x	X	x	x	x
Continue for all graded parameters							
N = number of subjects in the As Treated Population with any post-baseline data available for the specified Lab Parameter.							
n = number of subjects in the As Treated Population with treatment emergent abnormalities for the specified Lab Parameter.							
A treatment emergent laboratory abnormality is defined as a post-baseline abnormal value with a severity grade greater than at baseline.							

Table 90: Summary Statistics of Laboratory Results by Parameter, Study Visit Day, and Treatment Group – As Treated Population, Actual Baseline Ordinal Score 5 or 6

Laboratory Parameter	Study Visit Day	Treatment Group	Absolute					Change from Baseline				
			N	Mean	95% CI	Median	Min, Max	N	Mean	95% CI	Median	Min, Max
Parameter 1	Baseline	Baricitinib + PBO + RDV	x	xx.x	xx.x, xx.x	xx.x	xx.x, xx.x	---	---	---	---	---
		PBO + Dexamethasone + RDV	x	xx.x	xx.x, xx.x	xx.x	xx.x, xx.x	---	---	---	---	---
	Day 3	Baricitinib + PBO + RDV	x	xx.x	xx.x, xx.x	xx.x	xx.x, xx.x	x	xx.x	xx.x, xx.x	xx.x	xx.x, xx.x

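### Table 88's footnote makes the whole As Treated Population the denominator for by-visit Grade 3/4 laboratory percentages, although post-baseline labs exist only for subjects in hospital or seen in person

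*SAP*

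**What the plan says.** Table 88 in SAP Appendix 1 shows, by arm, the number and percentage of subjects with Grade 3, Grade 4 and Grade 3 or 4 laboratory results. There are rows for baseline and Days 3, 5, 8, 11, 15 and 29, and a row for maximum post-baseline severity. Each row has its own N column. The footnote reads: "N = Number of subjects in the As Treated Population". Section 6.3.2 says that this population "includes all randomized subjects who received the study product, even if only one dose was administered", so its size is fixed once dosing has begun.

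The laboratory data are not fixed in that way. Section 3.2 schedules post-baseline safety labs on "Days 3, 5, 8, and 11 (while hospitalized); and Days 15 and 29 (if attends in-person visit or still hospitalized"), and Section 9.6 says they are "collected Day 1, 3, 5, 8, 11 and Day 15 and 29 if able to return to clinic or still hospitalized". Section 4.1 allows the Day 15 and Day 29 visits to be held by phone, with no laboratory samples.

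The neighbouring tables use a different denominator:

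- Table 90, at the same visits: "N = Number of subjects in the As Treated Population with laboratory data available for the parameter at the specified study visit".
- Table 89, for maximum post-baseline grade: "N = number of subjects in the As Treated Population with any post-baseline data available for the specified Lab Parameter".
- Section 6.1, as the general rule for percentages: "the denominator (e.g. number of subjects with non-missing data) will be displayed".

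**The concern.** A subject with no blood draw at a visit has an unknown grade. Leaving that subject in the denominator and out of the numerator records the grade as below 3. Discharged subjects are not drawn on Days 3 to 11, subjects followed by phone are not drawn on Days 15 and 29, and subjects who have died are not drawn at all. All of them stay in N as the footnote is written.

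Two things follow. The percentage at a visit with incomplete testing is lower than the rate among subjects who were tested. And two arms with the same rate among tested subjects print different percentages if their shares tested differ. This trial compares two active anti-inflammatory regimens for their effect on clinical course, so the arms may well differ in time in hospital. Table 88 is the only planned table of Grade 3/4 laboratory percentages by visit.

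**Working it through.** The SAP gives no figure for Table 88, so there is none to reproduce. The check is an identity plus illustrations.

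**Identity.** Let A be the number in the As Treated Population, T the number with a result at the visit, and n the number with a Grade 3/4 result.

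Printed rate = n / A = (T / A) × (n / T) = share tested × rate among tested.

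The printed rate equals the rate among tested only when T = A.

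**Dilution.** Take A = 750 per arm, which is half of the approximately 1500 planned in Section 5 (equal allocation is my assumption). Assume 50% are tested and 10% of those have a Grade 3/4 result. Then T = 375 and n = 37.5. The footnote gives 37.5 / 750 = 5%, while the data-available denominator gives 37.5 / 375 = 10%. Over a range of assumed values, the footnote's N prints:

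| Share tested | Rate among tested 5% | 10% | 20% |
|---|---|---|---|
| 100% | 5.0% | 10% | 20% |
| 80% | 4.0% | 8% | 16% |
| 50% | 2.5% | 5% | 10% |
| 30% | 1.5% | 3% | 6% |
| 20% | 1.0% | 2% | 4% |

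**Arm difference at equal toxicity.** Assume 10% among tested in both arms. As a rough proxy for the share still in hospital, use exp(−ln 2 × t / median), where t is days since randomization and the medians are the ACTT-2 times to recovery quoted in SAP Section 2.

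- Overall medians, 7 and 8 days. Day 8 (t = 7): shares 0.500 and 0.545, printed 5.0% and 5.5%. Day 11 (t = 10): shares 0.371 and 0.420, printed 3.7% and 4.2%.
- High-flow oxygen or non-invasive ventilation subgroup, 10 and 18 days. Day 8: shares 0.616 and 0.764, printed 6.2% and 7.6%. Day 11: shares 0.500 and 0.680, printed 5.0% and 6.8%.

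Section 13 rounds percentages to whole numbers. The overall pairs would then both read 5% and 5% (Day 8) and 4% and 4% (Day 11). The Day 11 subgroup pair would read 5% and 7%. I give no Day 15 or Day 29 illustration, because the SAP gives no basis for the share attending in person.

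**The case against.** **The footnote may only be loose wording.** Table 88 prints N on every row, as Table 90 does. Shells with a constant N, such as Tables 79 and 87, put it in the arm header. The footnote also omits the title's restriction to baseline score 5 or 6. A visit-specific N may well have been intended. This stands as a reading of intent, but it is a reason to correct the footnote: a programmer who follows it as written produces the diluted percentages, and an example in Section 6.1 does not override a table's own definition.

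**The tested-only rate is not the true rate.** This stands. Remaining in hospital is a post-randomization outcome, and those who remain are sicker. Suppose 38 subjects in each arm have a Grade 3/4 result, with 375 tested in one arm and 409 in the other (0.545 × 750). The As Treated denominator gives 38 / 750 = 5.1% in both arms; the tested denominator gives 38 / 375 = 10.1% against 38 / 409 = 9.3%. The arm that discharges sooner now looks worse. Each denominator answers a different question, so both should be visible.

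**The information can be found elsewhere.** This stands in part. Table 90 gives the number with data by parameter, visit and arm, Table 89 gives maximum grades among those with data, and Listing 23 gives every result. A reader could rebuild the percentage for a single parameter, but Table 90 has no block matching Table 88's any-parameter rows.

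**Readings that go too far.** A reader might infer that the printed rates reflect discharge rather than toxicity; they reflect both. A reader might infer that dilution must be worse at Days 15 and 29. The SAP does not support that: Section 4.1 prefers in-person visits on those days so that safety labs can be drawn, and the share tested could rise. A reader might also object that the maximum-severity row takes results "including unscheduled assessments and assessments beyond Day 29". That scope is openly stated. A cut at actual Day 29 could discard labs from an in-window Study Visit Day 29 held later, which Section 3.3.2 allows.

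**Conclusion.** The point holds as a defect in the Table 88 footnote. As written, it counts untested subjects as having no Grade 3/4 abnormality and departs from Tables 89 and 90 and from the Section 6.1 example. The dilution equals the share tested; at an assumed 50% tested it is two-fold, from 10% to 5%.

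The arm difference is much less certain. Under the overall ACTT-2 proxy it is about half a percentage point and disappears on rounding; under the subgroup proxy it is up to about two points. Those figures assume equal allocation, a 10% rate among tested, exponential recovery, and recovery as a stand-in for discharge, although recovery includes Category 3, which is still in hospital. The ACTT-2 control was also remdesivir plus placebo, not dexamethasone.

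The baseline row is little affected, and the maximum-severity row only through subjects with no post-baseline result. Table 88 carries no test, interval or decision rule, so the primary analysis and its type I error are untouched. The correction is still worth making because it changes printed safety percentages at almost no cost.

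**What to change.** Replace the Table 88 footnote on N with:

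- For each time point: the number of As Treated subjects with actual baseline ordinal score 5 or 6 who have a result for the parameter at that time point. For the any-parameter block, those with a result for at least one graded parameter.
- For the maximum-severity row: the number of those subjects with any post-baseline result for the parameter. Leave the row's stated time scope as it is.

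Show the As Treated total (baseline score 5 or 6) for each arm in the header, so that both denominators are visible. Add a note that by-visit percentages are conditional on being tested and that the subjects tested change over time with discharge, death and attendance.

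The cost is a footnote edit, one header count and a small programming change. No new data are needed. By-visit percentages will be higher than under the present footnote wherever testing is incomplete.
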